9.5 Appendix E Severity Grading of Laboratory Abnormalities

Serum*	Mild (Grade 1)	Moderate (Grade 2)	Severe (Grade 3)	Potentially Life Threatening (Grade 4)**
Sodium – Hyponatremia mEq/L	132 – 134	130 – 131	125 – 129	< 125
Sodium – Hypernatremia mEq/L	144 – 145	146 – 147	148 – 150	> 150
Potassium – Hyperkalemia mEq/L	5.1 – 5.2	5.3 – 5.4	5.5 – 5.6	> 5.6
Potassium – Hypokalemia mEq/L	3.5 – 3.6	3.3 – 3.4	3.1 – 3.2	< 3.1
Glucose – Hypoglycemia mg/dL	65 – 69	55 – 64	45 – 54	< 45
Glucose – Hyperglycemia Fasting – mg/dL Random – mg/dL	100 – 110 110 – 125	111 – 125 126 – 200	>125 >200	Insulin requirements or hyperosmolar coma
Blood Urea Nitrogen (BUN) mg/dL	23 – 26	27 – 31	> 31	Requires dialysis
Creatinine – mg/dL	1.5 – 1.7	1.8 – 2.0	2.1 – 2.5	> 2.5 or requires dialysis
Calcium – hypocalcemia mg/dL	8.0 – 8.4	7.5 – 7.9	7.0 – 7.4	< 7.0
Calcium – hypercalcemia mg/dL	10.5 – 11.0	11.1 – 11.5	11.6 – 12.0	> 12.0
Magnesium – hypomagnesemia mg/dL	1.3 – 1.5	1.1 – 1.2	0.9 – 1.0	< 0.9
Phosphorous – hypophosphatemia mg/dL	2.3 – 2.5	2.0 – 2.2	1.6 – 1.9	< 1.6
CPK – mg/dL	1.25 – 1.5 x ULN***	1.6 – 3.0 x ULN	3.1 – 10 x ULN	> 10 x ULN
Albumin – Hypoalbuminemia g/dL	2.8 – 3.1	2.5 – 2.7	< 2.5	--
Total Protein – Hipoproteinemia g/dL	5.5 – 6.0	5.0 – 5.4	< 5.0	--
Alkaline phosphate – increase by factor	1.1 – 2.0 x ULN	2.1 – 3.0 x ULN	3.1 – 10 x ULN	> 10 x ULN
Liver Function Tests –ALT, AST increase by factor	1.1 – 2.5 x ULN	2.6 – 5.0 x ULN	5.1 – 10 x ULN	> 10 x ULN
Bilirubin – when accompanied by any increase in Liver Function Test increase by factor	1.1 – 1.25 x ULN	1.26 – 1.5 x ULN	1.51 – 1.75 x ULN	> 1.75 x ULN
Bilirubin – when Liver Function Test is normal; increase by factor	1.1 – 1.5 x ULN	1.6 – 2.0 x ULN	2.0 – 3.0 x ULN	> 3.0 x ULN
Cholesterol	201 – 210	211 – 225	> 226	---
Pancreatic enzymes – amylase, lipase	1.1 – 1.5 x ULN	1.6 – 2.0 x ULN	2.1 – 5.0 x ULN	> 5.0 x ULN

* The laboratory values provided in the tables serve as guidelines and are dependent upon institutional normal parameters. Institutional normal reference ranges should be provided to demonstrate that they are appropriate.

** The clinical signs or symptoms associated with laboratory abnormalities might result in characterization of the laboratory abnormalities as Potentially Life Threatening (Grade 4). For example, a low sodium value that falls within a Grade 3 parameter (125-129 mE/L) should be recorded as a Grade 4 hyponatremia event if the participant had a new seizure associated with the low sodium value.

***ULN" is the upper limit of the normal range.

Hematology *	Mild (Grade 1)	Moderate (Grade 2)	Severe (Grade 3)	Potentially Life Threatening (Grade 4)
Hemoglobin (Female) - mg/dL	11.0 – 12.0	9.5 – 10.9	8.0 – 9.4	< 8.0
Hemoglobin (Female) change from baseline value - mg/dL	Any decrease – 1.5	1.6 – 2.0	2.1 – 5.0	> 5.0
Hemoglobin (Male) - mg/dL	12.5 – 13.5	10.5 – 12.4	8.5 – 10.4	< 8.5
Hemoglobin (Male) change from baseline value – mg/dL	Any decrease – 1.5	1.6 – 2.0	2.1 – 5.0	> 5.0
WBC Increase - cell/mm ³	10,800 – 15,000	15,001 – 20,000	20,001 – 25, 000	> 25,000
WBC Decrease - cell/mm ³	2,500 – 3,500	1,500 – 2,499	1,000 – 1,499	< 1,000
Lymphocytes Decrease - cell/mm ³	750 – 1,000	500 – 749	250 – 499	< 250
Neutrophils Decrease - cell/mm ³	1,500 – 2,000	1,000 – 1,499	500 – 999	< 500
Eosinophils - cell/mm ³	650 – 1500	1501 - 5000	> 5000	Hypereosinophilic
Platelets Decreased - cell/mm ³	125,000 – 140,000	100,000 – 124,000	25,000 – 99,000	< 25,000
PT – increase by factor (prothrombin time)	1.0 – 1.10 x ULN**	1.11 – 1.20 x ULN	1.21 – 1.25 x ULN	> 1.25 ULN
PTT – increase by factor (partial thromboplastin time)	1.0 – 1.2 x ULN	1.21 – 1.4 x ULN	1.41 – 1.5 x ULN	> 1.5 x ULN
Fibrinogen increase - mg/dL	400 – 500	501 – 600	> 600	--
Fibrinogen decrease - mg/dL	150 – 200	125 – 149	100 – 124	< 100 or associated with gross bleeding or disseminated intravascular coagulation (DIC)

* The laboratory values provided in the tables serve as guidelines and are dependent upon institutional normal parameters. Institutional normal reference ranges should be provided to demonstrate that they are appropriate.

** "ULN" is the upper limit of the normal range.

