^a Grade 4 AE includes any Grade 4 solicited local or systemic AR and any Grade 4 laboratory abnormality. Grading of laboratory parameters will be based on the US FDA Guidance for Industry "Toxicity grading scale for healthy adult and adolescent volunteers enrolled in preventive vaccine clinical trials" (DHHS 2007b).

Protocol: mRNA-1020-P101 Amendment 1 mRNA-1020 and mRNA-1030

Table 6: Pause Rule Criteria, Events, and Thresholds – Proportion of Participants

Pause Rule	Event	Number or Percentage of Participants ^a
5	Any Grade 3 solicited local AR lasting more than 48 hours, within the 7-day postvaccination period	≥ 2 ^b of the initial 12 participants or ≥ 20% of participants after the initial 12 participants have been enrolled
6	Any Grade 3 solicited systemic AR lasting more than 48 hours (24 hours for fever) that cannot be reasonably attributed to a cause other than vaccination, within the 7-day postvaccination period	$\geq 2^{\rm b}$ of the initial 12 participants or $\geq 20\%$ of participants after the initial 12 participants have been enrolled
7	Any severe unsolicited AE in a vaccination group that cannot be reasonably attributed to a cause other than vaccination OR Any Grade 3 laboratory abnormality ^c in a vaccination group that cannot be reasonably attributed to a cause other than vaccination	≥ 2 ^b of the initial 12 participants or ≥ 20% of participants after the initial 12 participants have been enrolled

Abbreviations: AE = adverse event; AR = adverse reaction; FDA = Food and Drug Administration; MedDRA = Medical Dictionary for Regulatory Activities; US = United States.

If a pause is triggered in the study, each participant's study site visits will continue until EoS. If a pause affects a participant's vaccination visit, the window for that participant's vaccination visit will be suspended until the pause is lifted and vaccination can resume. Once the pause is lifted, vaccination should be reinstated as soon as possible.

If a participant is in the screening period for more than 28 days as the result of a pause, the participant may be rescreened for study eligibility (and will receive a new screening number) as long as the participant continues to provide consent to participate in the study.

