6.4.4 Clinical Laboratory Evaluations

Safety laboratory testing will include hematology and serum chemistry.

For continuous hematology and serum chemistry parameters, the observed values and changes from baseline will be summarized at each time point by vaccination group and then by age group as defined in [Section 6.2.9](#).

Summary of Grade 3+ laboratory abnormalities by visit and toxicity grades will be provided by vaccination group and then by age group as defined in [Section 6.2.9](#).

Hematology and chemistry toxicity grades will be summarized using a shift table from baseline to Day 8 by vaccination group.

All laboratory test results will be presented in the data listings. The results that are outside the reference ranges will be flagged in the data listings. The abnormalities meeting the toxicity grading criteria (Grade 3 or higher) in [Appendix E](#) in any safety laboratory (hematology and serum chemistry) will be listed separately.

A pregnancy test will be performed on all female participants of childbearing potential at the Screening Visit and before vaccine administration on Day 1 via point-of-care urine, and as needed at unscheduled visits (urine or blood pregnancy test based on the investigator's discretion).

The pregnancy test results will be listed.

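### SAP Appendix E labels all four hemoglobin grading rows in mg/dL, but the cut-offs make sense only in g/dL: a 1000-fold unit error in the SAP's only laboratory toxicity scale

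*SAP*

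**What the plan says.** The hematology part of SAP Appendix E has four hemoglobin rows, all in the same unit:

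- "Hemoglobin (Female) - mg/dL": Grade 1 11.0 to 12.0, Grade 2 9.5 to 10.9, Grade 3 8.0 to 9.4, Grade 4 below 8.0.
- "Hemoglobin (Male) - mg/dL": Grade 1 12.5 to 13.5, Grade 2 10.5 to 12.4, Grade 3 8.5 to 10.4, Grade 4 below 8.5.
- "Hemoglobin (Female) change from baseline value - mg/dL" and "Hemoglobin (Male) change from baseline value – mg/dL": Grade 1 any decrease up to 1.5, Grade 2 1.6 to 2.0, Grade 3 2.1 to 5.0, Grade 4 above 5.0.

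The serum part of the same appendix uses g/dL for two other proteins, "Albumin – Hypoalbuminemia g/dL" and "Total Protein – Hipoproteinemia g/dL".

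SAP section 6.4.4 puts the scale to use: "The abnormalities meeting the toxicity grading criteria (Grade 3 or higher) in" Appendix E are to be listed separately. The same section plans a summary of Grade 3+ laboratory abnormalities by visit and a shift table of toxicity grades from baseline to Day 8, without naming the scale for either. Hemoglobin is one of the eight safety tests in Protocol section 8.1.3, and laboratory abnormalities in the week after vaccination are a primary safety endpoint (SAP section 3.1). Neither document gives g/dL for hemoglobin anywhere.

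**The concern.** Appendix E is a working threshold table. A programmer derives grades from it, and those grades fill the safety outputs. With the unit wrong by a factor of 1000, a derivation that respects the printed unit fails in opposite directions in the two kinds of row: the absolute rows stop grading anything, and the change rows call almost every fall potentially life threatening. The outputs at stake are the grade-based hemoglobin displays that support a primary safety endpoint.

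**Working it through.** No derived figure in the plan needs reproducing, because the disputed item is a unit label. The check is a conversion, followed by grading example values under both readings.

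**Inputs.** The cut-offs and units are those printed in SAP Appendix E. The conversion is 1 g/dL = 1000 mg/dL.

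**Step 1: what the printed unit means.** Dividing by 1000:
- Female Grade 3: 8.0 to 9.4 mg/dL = 0.0080 to 0.0094 g/dL.
- Male Grade 3: 8.5 to 10.4 mg/dL = 0.0085 to 0.0104 g/dL.
- Highest absolute cut-off in any row: 13.5 mg/dL = 0.0135 g/dL.
- Grade 4 fall: above 5.0 mg/dL = above 0.005 g/dL.

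**Step 2: comparison within the appendix.** The appendix grades albumin as low at 2.5 to 3.1 g/dL (2,500 to 3,100 mg/dL) and total protein at 5.0 to 6.0 g/dL (5,000 to 6,000 mg/dL). It does use mg/dL for fibrinogen, which it grades as low at 100 to 200 mg/dL. As printed, a female hemoglobin at the top of Grade 1 (12.0 mg/dL) would be 12.0 / 150 = 8% of the lower bound of Grade 1 low fibrinogen. With g/dL the same numbers become 8,000 to 9,400 mg/dL (female Grade 3) and 8,500 to 10,400 mg/dL (male Grade 3), and nothing else in the rows needs to change.

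**Step 3: grading example values both ways.**

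| Result | In mg/dL | Grade, unit as printed | Grade, g/dL |
|---|---|---|---|
| Female, 7.5 g/dL | 7,500 | none | 4 |
| Female, 9.0 g/dL | 9,000 | none | 3 |
| Female, 10.0 g/dL | 10,000 | none | 2 |
| Female, 11.5 g/dL | 11,500 | none | 1 |
| Fall of 0.1 g/dL | 100 | 4 | 1 |
| Fall of 1.5 g/dL | 1,500 | 4 | 1 |
| Fall of 2.1 g/dL | 2,100 | 4 | 3 |
| Fall of 5.1 g/dL | 5,100 | 4 | 4 |

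Under the printed unit every realistic absolute value is ungraded, and every fall of 0.1 g/dL or more is Grade 4.

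**Step 4: where the grades go.** SAP section 6.4.4 names Appendix E for the Grade 3+ listing. The Grade 3+ summary and the shift table need a scale, and the SAP contains no other for laboratory values, so their use of Appendix E is an inference, though a natural one. The summaries of observed values and changes in section 6.4.4, the flags for results outside reference ranges, and the tabulation against normal ranges in Protocol section 9.5.2 do not use grades and are untouched.

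**Step 5: the pause rules and eligibility.** Footnote a to Protocol Table 5 says "Grade 4 AE includes any Grade 4 solicited local or systemic AR and any Grade 4 laboratory abnormality", but its next sentence ties laboratory grading to the FDA guidance. Footnote c to Table 6 does the same for Grade 3 laboratory abnormalities. Neither refers to the SAP. Exclusion criterion 2 excludes laboratory values above Grade 1 and does not cite Appendix E.

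**The case against.** The strongest reply is that nothing may go wrong in practice. If the central laboratory reports hemoglobin in g/dL and the programmer applies the printed numbers directly, every grade is correct. The intended unit is obvious from the size of the numbers, and a literal application would show itself at once as a flood of Grade 4 falls. Much of this stands: the effect on outputs is conditional on conversion to the printed unit, and neither document describes such a step. But neither document states the reporting unit either, and only the change rows fail loudly. The absolute rows fail quietly. In healthy adults screened for laboratory abnormalities, a table with no Grade 3+ absolute hemoglobin values would look unremarkable.

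The Appendix E footnote that calls the values guidelines, dependent on institutional normal ranges, does not help. It allows for local reference ranges, not for a unit that is wrong by a factor of 1000.

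In the other direction, a reader might infer that the error could trigger pauses, since one Grade 4 laboratory abnormality can meet pause rule 2. The documents do not support that. Pause-rule laboratory grading cites the FDA guidance directly, and rule 2 also requires that the event cannot reasonably be attributed to another cause. SAP section 1 says the SAP prevails where its methods differ from the protocol's, but that clause concerns analysis methods, and no SAP section applies Appendix E to the pause rules. Any count of participants per arm misgraded as Grade 4 would need a rate of hemoglobin falls at Day 8 that the documents do not give.

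**Conclusion.** The point holds as a unit-label error in four rows of SAP Appendix E, by a factor of exactly 1000. The numbers themselves are coherent once read as g/dL. That g/dL is intended rests on the magnitude of the numbers and on the appendix's own g/dL rows for albumin and total protein; the cited guidance was not available to check.

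The reach is the SAP's grade-based laboratory outputs: the Grade 3+ listing by explicit reference, and the Grade 3+ summary and Day 8 shift table by inference. The size depends on one unstated fact. If results are graded in the printed unit, all realistic absolute hemoglobin values are ungraded and all falls of 0.1 g/dL or more are Grade 4. If g/dL results are compared directly with the printed numbers, no grade changes. An effect on pausing or eligibility is not shown. The correction is still worth making, because the table is wrong as written, serves a primary safety endpoint and costs almost nothing to put right.

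**What to change.** In SAP Appendix E, change mg/dL to g/dL in the four hemoglobin rows (female and male, absolute and change from baseline) and leave the cut-offs as they are. Before the grade-based outputs are programmed, confirm the Appendix E units against the central laboratory's reporting units. It would also help to name Appendix E in section 6.4.4 as the scale for the Grade 3+ summary and the shift table. The cost is four labels, one sentence and one check of units. No data collection, sample size or analysis method changes.

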9.6 Appendix F Severity Grading of Vital Sign Abnormalities

Vital Signs*	Mild (Grade 1)	Moderate (Grade 2)	Severe (Grade 3)	Potentially Life Threatening (Grade 4)
Fever (°C)** (°F)**	38.0 – 38.4 100.4 – 101.1	38.5 – 38.9 101.2 – 102.0	39.0 – 40 102.1 – 104	> 40 > 104
Tachycardia - beats per minute	101 – 115	116 – 130	> 130	ER visit or hospitalization for arrhythmia
Bradycardia - beats per minute***	50 – 54	45 – 49	< 45	ER visit or hospitalization for arrhythmia
Hypertension (systolic) - mm Hg	141 – 150	151 – 155	> 155	ER visit or hospitalization for malignant hypertension
Hypertension (diastolic) - mm Hg	91 – 95	96 – 100	> 100	ER visit or hospitalization for malignant hypertension
Hypotension (systolic) – mm Hg	85 – 89	80 – 84	< 80	ER visit or hospitalization for hypotensive shock
Respiratory Rate – breaths per minute	17 – 20	21 – 25	> 25	Intubation

* Participant should be at rest for all vital sign measurements.

** Oral temperature; no recent hot or cold beverages or smoking.

*** When resting heart rate is between 60 – 100 beats per minute. Use clinical judgement when characterizing bradycardia among some healthy participant populations, for example, conditioned athletes.
